9.14.6 Other Observations Related to Safety

Not applicable.

9.15 Operational Futility Analysis

Tracking of confirmed events of MCI due to AD will be done on an ongoing basis, in a blinded fashion. A confirmed event of MCI due to AD requires two consecutive cases of MCI due to AD corresponding to two consecutive 6-month visits as adjudicated by the CIAC. The study will be declared to be "operationally futile" if the accrual of confirmed events is too slow to allow completion of the study in a feasible time frame.

Under the assumptions of the study, a projection has been made of when the target of 202 confirmed events (in the primary efficacy analysis population) of high-risk, non-Hispanic/Latino Caucasian subjects) will be achieved, as well as a corresponding last-subject-out (LSO) date.

The first assessment of operational futility will be done in April 2017. A maximum delay of up to 1 year in LSO is acceptable at the time of the first operational futility. If the projected LSO delay is 1 year or less at the time of operational futility, then the study will be considered as non-futile with respect to operational futility and will continue unchanged.

If the projected delay in LSO is greater than 1 year at the time of the first operational futility assessment, then a review of subjects with one case of MCI due to AD will be done to see whether or not it is feasible that within the next 6 months enough confirmed events of MCI due to AD are likely to accrue such that the delay in projected LSO date is less than or equal to 1 year. If not, then the study will be declared to be “operationally futile”.

If the first operational futility assessment in April 2017 indicates a projected delay in LSO of greater than 1 year but a review of subjects currently being tracked as part of the adjudication process indicates the study is not operationally futile, then a second assessment of operational futility will be done in October 2017, using decision rules analogous to those used for the first operational futility analysis. If the second assessment of operational futility is passed successfully (ie, is non-futile), no further assessments of operational futility are planned.

If operational futility is declared, then an early efficacy futility analysis (ie, prior to reaching 33% of planned events as described in Section 9.16 below) will be done as soon as practicable (ie, after all pertinent data for the futility analyses has been 100% cleaned and locked in the clinical database) and will be provided to the DSMB.

In the event of an early efficacy futility analysis triggered by a declaration of operational futility, the calculated value of conditional power (described below) will be provided to the DSMB: If the conditional power value of the primary efficacy futility analysis is $\leq 30\%$, then the DSMB will recommend that the study is futile with respect to efficacy; if the conditional power value is $>30\%$, then the DSMB may consider recommending that the trial is non-futile with respect to efficacy. The DSMB will then present their conclusions to the Executive Committee, who will decide whether or not the trial will be stopped for futility. (Note that any interim analyses will only be used to assess futility: No claim of efficacy will be made based on any interim analysis results in this study.)

9.16 Efficacy Futility Analysis

An analysis for futility for efficacy will be conducted once approximately 33% (66 out of 202) of the anticipated events (ie, conversions from cognitively normal status to adjudicated diagnosis of MCI due to AD, or to AD dementia) have occurred in the high-risk, Caucasian, non-Hispanic/Latino group. However, since the biomarker risk stratum information is blinded, the time of the futility analysis will be estimated using all subjects (both high-risk and low-risk) in the Caucasian, non-Hispanic/Latino group. Therefore, the efficacy futility analysis will occur when approximately 69 events have been confirmed through adjudication in the Caucasian, non-Hispanic/Latino group (including both high-risk and low-risk subjects). Note that no adjustment of the alpha level is required for an analysis for futility, and that for this study the results of the futility analysis will be considered to be non-binding with respect to efficacy for purposes of decision making around study continuation.

Because a review of unblinded data is involved, the DSMB will oversee this process.

Once the total number of target events for the futility analysis has been reached, the DSMB will be unblinded for a review of actual treatment groups with respect to the primary efficacy

endpoint (and potentially other analyses described below, as applicable); this review could take place at the next regularly-scheduled DSMB meeting, or at an ad hoc DSMB meeting.

The primary futility analysis will be conducted by the [CCI] Unblinded DSMB Statistician, based on the treatment effect within the high-risk, Caucasian, non-Hispanic/Latino group. The calculation is a test from a Cox proportional hazards survival model to evaluate a difference between the treatment groups (pioglitazone versus placebo) for the high-risk comparison at the time of the interim futility analysis. Additionally, Kaplan-Meier curves by treatment group (including low-risk placebo) will be provided for the primary analysis population of non-Hispanic/Latino Caucasian subjects. If the primary futility analysis indicates futility, then the [CCI] Unblinded DSMB Statistician will provide an additional set of secondary futility analyses (described below). The DSMB could then recommend study continuation to completion for the targeted number of events or recommend (based on pre-specified criteria documented in the SAP) that the study be considered futile with respect to the primary efficacy endpoint, high-risk comparison.

Immediately after the futility analysis data review meeting takes place, the DSMB recommendation regarding the continuation of the study will be promptly communicated to the DSMB Liaison. If the data indicate that study termination should be considered, the DSMB Liaison will promptly convene an ad-hoc meeting within the Takeda/Zinfandel alliance senior management (ie, the Executive Committee) to further discuss the results of the futility analyses and make the final decision as to whether or not to terminate the study. In a similar manner to the DSMB, the Executive Committee will be unblinded to the results of the futility analyses, will keep all futility analysis results and discussions strictly confidential, and will have no involvement with the daily project activities of the study or study team.

If the alliance Executive Committee decides to terminate the study as a result of the futility analyses, this decision will be promptly communicated to all the stakeholders including the AD-4833/TOMM40 project team, investigators, ethics committees, and regulatory agencies.

Specifics of the unblinded analyses to the DSMB (and to the Executive Committee, if applicable) are described below. The futility analysis will have two parts, to be assessed in a hierarchical manner:

- First, an unblinded analysis to determine futility based on lack of pioglitazone efficacy with respect to the primary efficacy endpoint will be provided to the DSMB.
- Second, if the conditional power value is $>30\%$ (see Section 9.16.1), then the DSMB will make a recommendation to the Executive Committee that the study is non-futile with respect to efficacy. In this case, the study will continue unchanged, and the Executive Committee will remain blinded.
- If the conditional power value is $\leq 30\%$, then the DSMB will receive the additional planned unblinded analyses (described below) from the [CCI] Unblinded Statistician.

- MMRM analyses by visit (including all visits for which at least 50% of the subjects have non-missing values) based on the composite score key secondary endpoint related to changes from baseline in cognition.
- MMRM analyses by visit (including all visits for which at least 50% of the subjects have non-missing values) based the following components of the composite score key secondary endpoint.
 - CVLT-II Long-Delay Free Recall
 - CVLT-II Short-Delay Free Recall
 - BVMT-R Delayed Recall
- MMRM analyses by visit (including all visits for which at least 50% of the subjects have non-missing values) for MMSE total score.
- Summary statistics by visit for all of the above-described CLVT-II, BVMT-R, CDR-SB, and MMSE total score continuous endpoints for all visits. For CDR-SB, visit will be derived using visit window defined in Section 9.1.3.
- CCI 
- For the longitudinal model, a linear trajectory model (SPM1L) will be used to model the change in the continuous efficacy endpoint over time. This model is chosen because the futility analysis is likely at an early stage of the disease development and treatment effect. Treatment and treatment*time will be included to evaluate the effect of treatment on the progression of the continuous efficacy endpoint. Values of the continuous endpoint will be used as the response in the model. Baseline value will be coded as the response at time 0. Other covariates (age, years of education, gender, and pooled center) that are included in the MMRM model for the change from baseline in the composite score will also be included in the longitudinal model.
- For the hazard rate model, number of intervals for the piecewise constant baseline hazard function will be selected using $AIC_{Surv|Long}$ [Ref. 2]. Treatment effect on the hazard function will be evaluated by including treatment as a fixed factor. Other covariates (age, years of education, gender, and pooled center) included in the primary CPH model will also be included. Conditional power will be calculated using the value of the t statistic for testing the treatment effect on the hazard rate.

- Following subgroup analyses on the primary efficacy endpoint will be performed when there are at least 20% of the total primary efficacy events in the futility analysis in a subgroup:
 - Gender (male vs. female)
 - APOE risk-status (Low, High – where High denotes carriage of at least one APOE ε4 allele)
 - Baseline MMSE (≤ 27 vs. ≥ 28)
- Following subgroup summaries and MMRM analyses on the change from baseline in the composite score, CVLT-II Long and Short Delay Free Recall, BVMT-R Delayed Recall and MMSE total score will be performed when there are at least 400 subjects in a subgroup:
 - Gender (male vs. female)
 - APOE risk-status (Low, High – where High denotes carriage of at least one APOE ε4 allele)
 - Baseline MMSE (≤ 27 vs. ≥ 28)
- If the conditional power value is $>10\%$ but $<30\%$, “progression” of the conditional power in terms of an increasing number of the events vs. total needed will be provided for the following information fractions: 10% (20 events), 20% (41 events) and 34% (69 events) will be provided. The events will be selected based on the time of the occurrence of the event relative to the first dose. When the evidence against the null hypothesis is accumulating, the conditional power should increase as the information fraction increases; however, if the CP does not change as the information fraction increases, it may be unlikely evidence against the null hypothesis is being accumulated. Essentially if CP remains flat across 10%, 20%, 30% of events, it makes it less likely that the null hypothesis would be rejected the null hypothesis at end of study.
- For each of the conditional power calculation in this analysis, at each cut-off day, subjects with confirmed event or censored on or prior to the cut-off day, time-to-event definition will follow the time to the primary event definition. Subjects with confirmed event after the cut-off day will be censored at the last scheduled or unscheduled visit date prior to the cut-off day. Subjects censored after the cut-off day, time-to-event is censored on the cut-off day.
- Any additional ad hoc analyses requested by the Executive Committee (which will be generated and provided by the CCI Unblinded Statistician).

The above list of additional planned unblinded analyses may be revised by the Executive Committee.

The DSMB will meet, discuss, and decide on a formal recommendation to the Executive Committee regarding continuation of the study with respect to efficacy. Subsequently, the Executive Committee will decide whether or not to stop the trial with respect to efficacy.

In all possible scenarios, the DSMB will clearly document for the Executive Committee whether or not the study appears to be futile, or non-futile, with respect to the conditional power threshold (described below) specified for the primary efficacy analysis.

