The sample size for this study is based on the event-driven analysis that is planned for comparing treatment groups within the high-risk stratum. For the purposes of this study, it is assumed that the placebo-treated non-Hispanic/Latino Caucasian subjects in the high-risk stratum will have an event rate of 15% over a 5-year period. This is more conservative than the 18% cited in the table, to assure adequate sample size. With an expected improvement of a reduction in event rate of 40%, the target event rate for the active treatment group will be 9% over 5 years. Furthermore, the following specifications are used: alpha=0.01, a 2-sided statistical test based on survival analysis, power=90%, annual dropout rate of 12% (or cumulative dropout rate of 47% over 5 years). In order to detect a difference of the specified magnitude ($\geq 40\%$ reduction in conversion rates over 5 years), at least 202 events must be observed during the course of the study in non-

Hispanic/Latino Caucasian subjects (primary analysis). Based on these assumptions and the fact that only non-Hispanic/Latino Caucasian subjects will be used for the primary analyses, a total of 2,346 non-Hispanic/Latino Caucasian subjects (1,173 on pioglitazone/1,173 on placebo) are required from the high-risk stratum for randomization.

Sample Size for the Phase 3 Study Based On Qualifying the Test Used to Stratify Subjects

While using data from the results of risk stratification and not a comparison between randomized groups, the same analysis as specified for comparing the treatment groups within the high-risk stratum will also be used to compare the two placebo groups (high-risk placebo and low-risk placebo). Thus, assuming that the placebo-treated subjects in the low-risk stratum will have a conversion rate of 4% over a 5-year follow-up period, then approximately 314 non-Hispanic/Latino Caucasian subjects identified as low-risk for the event are required in that stratum. While this number of subjects enrolled in the low-risk stratum will provide very high power (99% with $\alpha=0.01$) to validate the enrichment algorithm with the assumed 5-year conversion rates (ie, 15% vs. 4%).

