4. Additional summaries and analyses are added to evaluate the biomarker qualification performance. Key secondary endpoints and additional variables (only at the domain and composite score levels) will be summarized and analyzed using the data from placebo subjects who are classified into low and high risk groups.

Justification: These analyses will be helpful for the evaluation of the biomarker qualification performance and will be presented at the end of study.

5. At the time of the efficacy futility analysis, if the conditional power is $<30\%$, the following subgroup analyses will be performed on the primary efficacy endpoint: gender (male vs. female), APOE risk-status (low vs. high) and baseline MMSE (≤ 27 vs. ≥ 28). A particular subgroup analysis (e.g. female) will be performed only when there are at least 20% of the total primary events in the subgroup.

Justification: This addition is expected to be informative in the efficacy futility assessment when the conditional power based on the primary event is $<30\%$.

6. At the time of the efficacy futility analysis, if the conditional power is $<30\%$, the following subgroup summaries and MMRM analyses will be performed on the change from baseline in the composite score, CVLT-II Long and Short Delay Free Recall Correct, BVMT-R Delayed Recall and MMSE total score: gender (male vs. female), APOE risk-status (low vs. high) and baseline MMSE (≤ 27 vs. ≥ 28). The subgroup analysis will be performed only when there are at least 400 subjects in a subgroup.

Justification: This addition is expected to be informative in the efficacy futility assessment when the conditional power based on the primary event is $<30\%$.

7. At the time of the efficacy futility analysis, if the conditional power is $<30\%$, and the treatment effect on the change from baseline by visit in the composite score is statistically significant ($p\text{-value} < 0.05$), a joint model of the time-to-event data and the longitudinal composite score data will be fitted to estimate the association between the composite score and hazard rate of MCI due to AD over time during the treatment period. Details of this model are presented in Section 9.16.

Justification: This addition is expected to be informative in the efficacy futility assessment when the conditional power based on the primary event is $<30\%$.

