8.0 DETERMINATION OF SAMPLE SIZE

Background Information for Determining Sample Sizes

Using 73 years as the age at entry (+5 years = age 78), a conversion rate of around 18% over 5 years can be expected (see [Table 8.a](#)). This is based on:

- The TOMM40 rs10524523 allele frequencies from the Duke Alzheimer’s Disease Research Center (ADRC), Cache County, and Wisconsin cohorts.
- The assessment of peer-reviewed published incident MCI in normal individuals.
- The effect of APOE on the incidence of AD.

Table 8.a Conversion Rate Estimates Based on Analysis of 3 Cohorts, Cognitive Impairment Incidence, and Observed TOMM40 rs10524523 Allele Frequencies

TOMM40 rs10524523 Genotype	Duke Bryan ADRC Frequency	Wisconsin Frequency	Cache Frequency	Cohort Total Count	Age 78 (Proportion Converted)	
					Proportion	Number of Converted Subjects
L/L	0.05	0.04	0.02	189	0.53	100
VL/L	0.14	0.15	0.13	543	0.34	185
S/L	0.17	0.20	0.14	669	0.22	147
S/S	0.23	0.16	0.17	929	0.14	130
S/VL	0.31	0.31	0.36	1236	0.10	124
VL/VL	0.11	0.14	0.18	433	0.05	22
Total count = 3999					Total converted	708
					Overall conversion rate	0.177

Taking into account the age ranges that will be enrolled in the phase 3 study, a 5-year conversion rate of 15% will be assumed for non-Hispanic/Latino Caucasian placebo subjects within the high-risk stratum identified by the enrichment process. Based on the expected 5-year conversion rate of 15%, the time-to-event was modeled using an exponential mathematical model for planning the study sample size.

Similarly, a 5-year conversion rate of 4% will be assumed for non-Hispanic/Latino Caucasian placebo subjects within the low-risk stratum. Thus, it is important to recognize that this summary of the data demonstrates nearly a four-fold enrichment of events over the population rate using the risk algorithm.

Determination of Sample Size for the Phase 3 Study Based on the High-Risk Stratum

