The sample size for this study is based on the event-driven analysis that is planned for comparing treatment groups within the high-risk stratum. For the purposes of this study, it is assumed that the placebo-treated non-Hispanic/Latino Caucasian subjects in the high-risk stratum will have an event rate of 15% over a 5-year period. This is more conservative than the 18% cited in the table, to assure adequate sample size. With a clinically meaningful improvement of a reduction in event rate of at least 40%, the target event rate for the active treatment group will be 9% over 5 years. Furthermore, the following specifications are used: $\alpha=0.01$, a 2-sided statistical test based on survival analysis, power=90%, annual dropout rate of 12% (or cumulative dropout rate of 47% over 5 years). In order to detect a difference of the specified magnitude ($\geq 40\%$ reduction in conversion rates over 5 years), at least 202 events must be observed during the course of the study in non-Hispanic/Latino Caucasian subjects (primary efficacy analysis). Based on these assumptions and the fact that only non-Hispanic/Latino Caucasian subjects will be used for the primary analyses, a total of 2,346 non-Hispanic/Latino Caucasian subjects (1,173 on pioglitazone/1,173 on placebo) should be enrolled from the high-risk stratum for randomization.

Sample Size for the Phase 3 Study Based On Qualifying the Test Used to Stratify Subjects

While using data from the results of risk stratification and not a comparison between randomized groups, the same analysis as specified for comparing the treatment groups within the high-risk stratum will also be used to compare the two placebo groups (high-risk placebo and low-risk placebo). Thus, assuming that the placebo-treated subjects in the low-risk stratum will have a conversion rate of 4% over a 5-year follow-up period, then approximately 314 non-Hispanic/Latino Caucasian subjects identified as low-risk for the event should be enrolled in that stratum. This number of subjects enrolled in the low-risk stratum will provide very high power (99% with $\alpha=0.01$) to validate the enrichment algorithm with the assumed 5-year conversion rates (ie, 15% vs. 4%).

Sample Size for the vMRI Substudy

This substudy is not designed or powered to assess any quantitative changes in the brain. Based on clinical judgment, a sample size of 300 subjects is believed to be sufficient to evaluate possible qualitative changes in the brain via vMRI.

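### On the visible text, the joint-model conditional power rests on the treatment effect not carried by the composite score, so it does not predict the final Cox test and can err in either direction

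*SAP*

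**What the plan says.** SAP 4.0, item 7, adds the joint model to the efficacy futility analysis. Two conditions trigger it: CP below 30%, and a treatment effect on change in the composite with p<0.05. No direction is required. Its purpose is given as: "a joint model of the time-to-event data and the longitudinal composite score data will be fitted to estimate the association", meaning the association of the composite with the hazard of MCI due to AD.

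SAP 9.16 gives the model in two parts. In the longitudinal part, "Treatment and treatment*time will be included to evaluate the effect of treatment on the progression of the continuous efficacy endpoint". In the hazard part, treatment is a fixed factor alongside age, education, gender and pooled center. The hazard bullet ends: "Conditional power will be calculated using the value of the t statistic for testing the treatment effect on the hazard rate". The bullet that introduces the model is blacked out in SAP 9.16 and again in Appendix E.

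SAP 9.16.1 defines CP as the probability of rejecting the tested null hypothesis at the final analysis. It takes Z(t) as the Wald statistic from the Cox model and assumes that the population hazard ratio equals the one observed. SAP 9.9.3.2 gives that Cox model: treatment, center, gender, education and age, with no composite score. SAP 9.16 also requires the DSMB to document futility against the threshold set for the primary efficacy analysis. No threshold is attached to the joint-model CP.

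**The concern.** Treatment appears twice in the joint model: once in the composite trajectory and once directly in the hazard. If the trajectory feeds the hazard, the direct coefficient is what remains after the part acting through the composite has been taken out. The final test has no composite in it and so picks up both parts. A CP computed from the direct term alone answers a different question from the one in SAP 9.16.1, although it carries the same name and invites comparison with the same 30%.

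The part carried by the composite may not be small. Failure on the CVLT-II or BVMT-R is among the criteria for the event (SAP 9.9.4), and the same tests make up the composite's memory domain (SAP 9.9.7).

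What is at stake is discretionary. A CP at or below 30% means only that the study may be deemed futile, the result is non-binding, and the Executive Committee decides after the DSMB's recommendation. The secondary analyses inform that judgement, and SAP 4.0 justifies this one as informative for the futility assessment.

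**Working it through.** **Reproducing the plan's denominator.** The information fraction in CP divides by 202 events. SAP 8.0 says that the placebo group "will have an event rate of 15% over a 5-year period", that "the target event rate for the active treatment group will be 9% over 5 years", and that "the time-to-event was modeled using an exponential mathematical model for planning the study sample size". The exponential hazard ratio is ln(0.91)/ln(0.85) = 0.5803. With two-sided alpha 0.01, 90% power and 1:1 allocation, the Schoenfeld formula gives 4 × (2.5758 + 1.2816)² / (ln 0.5803)² = 200.97, so 201 events. This agrees with the plan's statement that "at least 202 events must be observed during the course of the study"; 202 events give 90.2% power. The critical value also reproduces: P(Z ≤ -2.576) = 0.0050.

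**CP formula (SAP 9.16.1).** CP = Φ[-(Z/√t + 2.576)/√(1-t)], with t = 66/202 = 0.3267, √t = 0.5716 and √(1-t) = 0.8205. Under 1:1 allocation Z ≈ ln(HR) × √66/2. CP = 30% corresponds to Z = -1.227 (HR 0.739), and CP = 20% to Z = -1.078 (HR 0.767).

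**Direct term only.** Let m be the share of the log-HR acting through the composite. With the same standard error, the direct-term statistic is (1-m) × Z. The SAP gives no value for m, so the values are assumed. A negative m means an adverse composite effect.

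For a total effect of HR 0.767, Z = -1.078:
- m = 25%: Z = -0.808; -(-0.808/0.5716 + 2.576)/0.8205 = -1.416; CP 7.8%.
- m = 50%: Z = -0.539; argument -1.991; CP 2.3%.
- m = -25%: Z = -1.347; argument -0.267; CP 39%.

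Other starting points:

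| Total HR | Total-effect CP | m = 25% | m = 50% | m = 75% | m = -25% |
|---|---|---|---|---|---|
| 0.75 | 25.9% | 10.2% | 2.9% | 0.6% | 49.0% |
| 0.80 | 11.4% | 4.6% | 1.5% | 0.4% | 23.5% |

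**Does the trigger fix the direction?** An illustrative simulation assumed 1,470 per arm, linear trajectories, a hazard log-coefficient of -1.8 per composite unit, the true trajectory as covariate, and the trigger of CP<30% with composite p<0.05. There were 220 runs per scenario, averaging 67 to 73 events.

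| Scenario | Mean log-HR, total / direct | Triggered runs | Mean CP when triggered, total / direct | Direct CP lower |
|---|---|---|---|---|
| Fully mediated benefit | -0.231 / -0.016 | 136 | 5.5% / 0.3% | 100% |
| About half mediated | -0.277 / -0.129 | 119 | 7.0% / 1.2% | 100% |
| Adverse composite, direct benefit | -0.124 / -0.309 | 168 | 3.6% / 26.1% | 1% |

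In the adverse case, 35% of triggered runs gave a direct-term CP above 30% although the primary CP was below it.

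**The case against.** The strongest reply is that the structure is not fully visible. The redacted bullet is the natural place to define how the composite enters the hazard and what treatment effect is meant. If the link is through subject-level random effects only, the longitudinal treatment terms do not enter the hazard and the coefficient is not net of the composite pathway. The stated purpose in SAP 4.0, an association between the composite score and the hazard, favours a trajectory link but does not prove it. This stands, and the point is conditional on it.

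Second, the total-effect CP is already in the plan. The primary analysis computes it first, formal futility is judged on it, and the joint-model figure has no threshold. This also stands: the formal status does not change.

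Third, a reader might infer that the error always runs toward futility whenever the model is fitted, and that the DSMB would take a supportive cognitive signal as evidence for stopping. The documents support neither. The p<0.05 trigger has no direction, and a significant composite difference does not show that the composite affects the hazard. The DSMB also receives the repeated-measures results for the composite, its memory tests and the MMSE, so a favourable signal would be in view.

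Fourth, adding the two pathways does not give one number. With treatment-by-time in the trajectory, the combined effect changes over time. This limits the available remedy but does not rescue the planned statistic.

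**Conclusion.** The point holds on the visible text, assuming that the hazard depends on the composite trajectory. The joint-model figure is then not a conditional power in the sense of SAP 9.16.1, because it uses a different effect from the one the final Cox model tests. It understates CP when the composite effect is favourable and linked to lower hazard, and overstates it when the composite effect is adverse.

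The size cannot be fixed from the documents. The calculated figures rest on assumed mediated shares, equal standard errors and the approximation that direct and mediated parts add on the log-hazard scale. The simulation shows that direction-dependent error persists among triggered runs, under its own assumed parameters.

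The consequence is limited to a misleading secondary number in a non-binding, discretionary decision. It is worth correcting before the futility look because the correction is cheap and the figure invites comparison with 30%.

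**What to change.** Replace the last sentence of the hazard-model bullet in SAP 9.16. State that the primary Cox Wald statistic is the only basis for any CP compared with 30%, and that the joint-model treatment term is reported, with its confidence interval, as a direct-effect estimate that is not a CP. Report the association parameter and the treatment effect on the trajectory beside it, with their signs, so that the direction is plain.

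If a joint-model CP is still wanted, base it on the overall treatment effect: the direct term plus the association times the trajectory effect, averaged over time by a rule stated in advance, with a delta-method or bootstrap standard error. This remains only an approximation to what the Cox model estimates, which is a reason to prefer the first option.

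The first option costs a sentence or two of SAP text. The second adds a little post-processing of estimates that the model already produces and one more pre-specified choice, the averaging rule.
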